**NOTE: Step 2 entry may be deferred until further notice.**

After the last dose of study drugs, the post-treatment study visits have the following windows:

Step 1 (remote [via telephone] permitted, EXCEPT week 16):

- Study weeks 8 and 12, and 16: -5 days and +21 days
- **Study week 16: -5 days and +42 days**
- Study week 28: -7 days and +28 days

**NOTE: In the midst of the COVID-19 pandemic, for study week 28, all evaluations should be conducted remotely, and the week 28 specimen can be collected at a future date, prior to study closure, up until 36 weeks post treatment completion, as**

~~long as the week 16/SVR12 visit was conducted in person. Participants should only have the week 28 visit in person if the week 16/SVR12 visit and sample were missed.~~

~~If a participant has successfully attended the week 16/SVR12 visit and the blood sample has been collected, then that participant does not need to have an in-person visit at week 28.~~

Step 2 (~~deferred until further notice~~):

- Study week R+20, R+24, or R+28 (12 weeks after re-treatment completion for those not receiving RBV depends on Step 2 treatment duration): -5 days and +28 days
- Study week R+32, R+36, or R+40 completion (for those receiving RBV): -14 days and + 28 days

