## A Phase II Trial of Glecaprevir/Pibrentasvir Fixed-dose Combination Treatment for Acute Hepatitis C Virus Infection (PURGE-C)

DESIGN

This is a phase II single-arm, open-label study to assess the efficacy of a fixed dose combination (FDC) of glecaprevir/pibrentasvir (G/P) given for 4 weeks in acute hepatitis C (HCV)-infected participants, with and without HIV-1 coinfection.

The study has two steps:

Step 1: Four weeks of treatment for acute HCV infection and up to 24 weeks of follow-up. Post-treatment follow-up visits in Step 1 will occur at 4, 8, 12, and 24 weeks after the end of study treatment (G/P). Participants with HCV recurrence (reinfection, suspected relapse or undefined post-treatment viremia) or HCV virologic failure before or at the week 16/SVR12 (sustained virologic response 12 weeks post-treatment) visit during Step 1 will be eligible for re-treatment (Step 2).

Step 2: Re-treatment will be with G/P with or without ribavirin (RBV) for up to 16 weeks. Post-treatment follow-up for Step 2 will include visits for SVR12 determination.

DURATION

Up to 28 weeks in Step 1: 4 weeks on treatment and 24 weeks of post-treatment follow-up.

Up to 40 weeks in Step 2: up to 16 weeks of re-treatment and up to 24 weeks of post-treatment follow-up.

SAMPLE SIZE

Minimum of 44 participants, including at least 10 participants living with HIV-1 co-infection. If a participant discontinues early for reasons unrelated to study treatment and is not evaluable for SVR12 while registration is ongoing, then an additional participant may be enrolled as determined by the study team to attain an adequate number for key supporting analysis on SVR12. Additional enrollment may occur more than once, up to maximum enrollment of 50 participants.

POPULATION

Men and women age  $\geq 18$  years with acute HCV-infection (may be first HCV infection or re-infection) of any genotype, living with or without HIV-1 co-infection.

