## **2.4 Overview of Sample Size Considerations**

The study is designed to conclude with reasonable evidence that the true SVR12 proportion is greater than 80% in the study population. This will be assessed by examining if a two-sided 90% confidence interval (CI) for the sample proportion is entirely above 80%. This is equivalent to showing that the SVR12 proportion is higher than 80% in a one-sided test with a type I error of 5%. With 44 participants, there is at least 90% power to show that proportion achieving SVR12 is greater than 80% in a one-sided exact binomial test with a targeted significance level of 5%. The true SVR12 proportion is assumed to be 95%, when treated with 4 weeks of the G/P regimen. With a sample size of 44 participants, the Wilson confidence interval for the true SVR12 proportion will be entirely above 80% if 40 or more participants achieve SVR12 out of 44 participants.

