### 4.2 Analysis Approaches

- For the primary analysis:
  - As described in Section 3.1 above on Primary Outcome Measures, if a participant does not have any HCV RNA measurements in the SVR12 visit window, then the participant will be considered SVR12 failure, unless there are preceding and subsequent HCV RNA measurements that are both LLOQ (either TD or TND). The latest available preceding and the earliest available subsequent HCV RNA measurements around the targeted SVR12 visit window will be used. **If the participant's visit schedule was affected by COVID-19 as outlined in CM #2 and (1) only one HCV RNA sample is available after the study treatment, and (2) the sample is collected after the SVR12 visit window, then this result will be used as the primary outcome.**
  - Otherwise, not achieving unquantifiable HCV RNA at the study visit corresponding to the SVR12 evaluation will be considered failure for SVR12 determination in the primary analysis regardless of the reason. As such, early discontinuation of the study prior to the SVR12 visit and reinfection prior to the SVR12 visit will be considered a failure.
  - For the SVR12 analysis, a supplementary analysis will be conducted in the analysis set that excludes (1) participants who discontinued the study for reasons not related to the study treatment, and (2) participants who became re-infected with HCV prior to SVR12 visit. Reasons not related to study treatment may include, but are not limited to: participant moved away, participant cannot get to the clinic, participant cannot be located.
- All available data for the indicated study visits from the participants who initiate the study treatment will be used in the analysis, and the number of participants with available data will be specified for each analysis.
- Confidence intervals around proportions will be provided using the Wilson method for binomial data.

- Subgroup analyses based on the screening HIV infection status will be conducted for the HCV RNA analyses to address Secondary Objective 3.

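### Apart from re-infection, the supplementary SVR12 set removes a missing result only if the participant left the study; an unrescued missing result in someone still on study stays in, by implication as a failure

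*SAP*

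**What the plan says.** Four places define the supplementary set: SAP 4.2, SAP Section 5 item 9b, and protocol 10.1 and 10.6. All use two exclusions. One is leaving the study for reasons unrelated to treatment; in SAP 4.2 the set "excludes (1) participants who discontinued the study for reasons not related to the study treatment". The other is HCV re-infection before the SVR12 visit. The examples of unrelated reasons are moving away, being unable to reach the clinic and being impossible to locate.

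For a participant with no HCV RNA in the SVR12 window, SAP 4.2 says "then the participant will be considered SVR12 failure, unless there are preceding and subsequent HCV RNA measurements" that are both below LLOQ. SAP 3.1 allows weeks 8, 12 and 28 and unscheduled samples to serve. SAP 4.2 adds one more rescue: if the visit schedule was affected as described in CM #2, a single post-treatment sample taken after the window is used as the outcome. CM #2 limits itself to the 10 participants enrolled by March 18, 2020.

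Protocol 10.6 says the supplementary analysis follows methods similar to those of the primary. The SAP gives it no missing-data rule of its own.

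LOA #3 sets the post-treatment visits as "Step 1 (remote [via telephone] permitted, EXCEPT week 16", widens the week 16 window to -5/+42 days, and in Section 6.3.21 postpones research bloods until the participant can return. The schema allows a replacement for someone who discontinues early for an unrelated reason and "is not evaluable for SVR12 while registration is ongoing".

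**The concern.** The two exclusions exist to show SVR12 without failures that reflect only a lost outcome or a new infection. Exclusion (1) does this only when the lost outcome comes with an off-study record. Take two participants who could not get to the clinic for the week 16 blood and have no rescue. The one taken off study leaves the denominator. The one who stayed, perhaps completing week 28 by telephone, remains in it with a result that defaults to failure. The better-retained participant counts against the regimen.

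Protocol 10.1 gives this analysis real weight: it allows up to 6 extra participants so that it is well powered. Replacement is also tied to discontinuation, so a missing result in someone still on study is neither excluded nor replaced. The estimate then depends partly on how sites record an absent participant.

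**Working it through.** **1. Inputs (SAP 2.4).** The target is to show that "the true SVR12 proportion is greater than 80% in the study population". The test is "examining if a two-sided 90% confidence interval (CI) for the sample proportion is entirely above 80" per cent. On size and power: "With 44 participants, there is at least 90% power to show that proportion achieving SVR12 is greater than 80" per cent, where "The true SVR12 proportion is assumed to be 95" per cent. The stated success rule is 40 or more of 44.

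**2. Reproducing the plan.** The Wilson limits for x successes in n, with p = x/n and z = 1.645 (z² = 2.706), are

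[p + z²/(2n) ± z·√(p(1−p)/n + z²/(4n²))] / (1 + z²/n).

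- 40/44: centre 0.8854, half-width 0.0731, so 81.2 to 95.9, as in protocol Table 10.4-2.
- 39/44: centre 0.8640, half-width 0.0796, so 78.4 to 94.4, also as in that table.
- P(X ≥ 40 | n = 44, p = 0.95) = 0.933, against 93% in Table 10.4-1. Under p = 0.80 it is 0.044.

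**3. Who is affected.** An on-study participant falls into the gap only if all three of these hold:

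- no HCV RNA in the week 16 window, which LOA #3 makes 5 + 42 = 47 days wide around the target;
- no pair of results below LLOQ on either side of it;
- no late sample accepted under the CM #2 rule.

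One route is a missed week 16 draw followed by a week 28 telephone visit whose postponed blood is never taken. Another is remote visits at weeks 8 and 12 that leave only a late result with nothing before it. CM #2 covers 10 participants, so on its text 44 − 10 = 34 later enrollees would not have the late-sample rescue. No rate is given; I assume k = 0 to 3.

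**4. One participant's study status.** Assume 44 treated, 39 below LLOQ, 4 relapses, 1 missing for an unrelated reason (39 + 4 + 1 = 44).

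- Stayed on study: 39/44 = 88.6%, interval 78.4 to 94.4.
- Taken off study: 39/43 = 90.7%, centre 0.8829, half-width 0.0747, interval 80.8 to 95.8.

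**5. Two participants.** Assume 38 below LLOQ, 4 relapses, 2 missing (38 + 4 + 2 = 44).

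- Both stayed: 38/44 = 86.4%, 75.7 to 92.8.
- One left: 38/43 = 88.4%, 78.0 to 94.2.
- Both left: 38/42 = 90.5%, 80.4 to 95.7.

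**6. Chance that the supplementary interval clears 80%**, with true SVR12 of 95% among the 44 − k observed:

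| k | Kept as failures (40 successes needed) | Removed (Wilson cut-off) |
|---|---|---|
| 0 | 93.3% | 93.3% (40/44) |
| 1 | 83.3% | 93.8% (39/43) |
| 2 | 64.9% | 94.3% (38/42) |
| 3 | 38.6% | 85.3% (38/41) |

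With removal, the exact one-sided error at 80% is 0.051, 0.058 and 0.024 for k = 1, 2 and 3.

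**The case against.** The strongest reply is that the rule is deliberate and conservative. In an open-label single-arm trial, limiting removals to recorded discontinuations limits discretion, and the replacement rule also requires discontinuation. Why a sample is missing is harder to establish for someone still on study, and a non-attender's viral status is unknown. That stands as a cost of the fix. It does not explain why the same judgement is accepted for someone who left.

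Several stronger readings are tempting, and the documents do not support them:

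- A reader might infer that discontinuation is the only exclusion. Re-infection is excluded too.
- A reader might infer that every on-study participant without week 16 blood counts as a failure. The bracketing and CM #2 rules rescue some.
- A reader might infer that telephone visits mean no HCV RNA. LOA #3 postpones research bloods rather than waiving them, requires week 16 blood, and accepts a visit for blood only. Protocol 6.3.18 and 6.3.19 add locator updates and a reminder.
- A reader might infer that failure scoring in this set is stated. It is inferred from protocol 10.6 and the general rule. SAP 4.2 also promises the number with available data for each analysis, and detail is left to an Analysis Implementation Plan that I have not seen.
- A reader might infer that a formal trial conclusion flips. The 80% conclusion rule is in item 9a; item 9b only assesses SVR12. The examples sit at the boundary: with 40 successes, 40/44 already has a lower limit of 81.2%. On an exact one-sided test, 39/43 (p = 0.051) and 38/42 (p = 0.058) do not reach 5%.

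Protocol 10.1 also requires reasons for SVR failure to be described, so a reader could recompute.

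**Conclusion.** The point holds in a limited form. Followed as written, the supplementary set treats two participants with the same reason and the same missing result differently according to study status alone, which works against its purpose. That the retained participant is scored as a failure is an implication, not an explicit statement.

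The number affected is unknown and probably small. With k from 0 to 3 (an assumption), one participant matters only near the boundary, as 39/44 against 39/43 shows; further from it the reading does not change. The power figures additionally assume N = 44, true SVR12 of 95% in those observed, and clearing 80% as the yardstick for this analysis. A firm claim of downward bias would require that missing results carry no information about response, which the documents do not establish. The primary analysis is not in question, because missing = failure is a deliberate choice there. This is a cheap improvement to a named and powered analysis.

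**What to change.** In SAP 4.2 and item 9b, with matching wording for protocol 10.1 and 10.6 so that the documents agree, redefine exclusion (1) along these lines: participants with no determinable SVR12 result (none in the window, no bracketing pair, no CM #2 late sample) for a documented reason clearly not related to study treatment, whether or not they discontinued the study.

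Add that a participant with quantifiable HCV RNA after the end of treatment, not classed as re-infection, stays in as a failure. State openly that this also keeps in some discontinuers whom the present text removes. Report the number excluded by on-study or off-study status and by reason. Leave the primary analysis as it is.

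The new wording also covers a smaller gap. SAP 4.2 omits protocol 10.1's limit to discontinuation before the SVR12 evaluation, so read literally it could drop someone who left after an observed week 16 result.

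The cost is a short edit in both documents, a slightly smaller supplementary denominator, and a judgement of relatedness for on-study missing results.

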Participants experiencing documented viral recurrence before or at the week 16 or SVR12 visit will proceed to Step 2 and be classified as either re-infection or suspected relapse, prior to re-treatment. The type of viral recurrence (suspected relapse versus re-infection) will be determined by the A5380 team chair, co-chairs, and virologist ([[contact]](mailto:[contact])) based initially on genotype/subtype information and resistance testing and then reported to the sites by email to inform them of the recommended re-treatment regimen for Step 2. If a re-infection, they will be re-treated with 8 weeks of FDC G/P. If a suspected relapse, they will be re-treated with a treatment regimen of 16 weeks of FDC G/P with or without weight-based RBV, irrespective of genotype. Participants experiencing virologic failure (failure to achieve HCV RNA <LLOQ and confirmed increase in HCV RNA  $>1 \log_{10}$  from nadir) will also proceed to Step 2 and will be re-treated with 16 weeks of FDC G/P with or without weight-based RBV. Participants experiencing post-treatment HCV viremia not otherwise defined as re-infection, suspected relapse or virologic failure will also proceed to Step 2 and will be re-treated with 16 weeks of FDC G/P with or without weight-based RBV. At the discretion of the site PI and upon discussion with the A5380 CMC ([[contact]](mailto:[contact])), participants experiencing suspected relapse, virologic failure, or undefined post-treatment HCV viremia may be re-treated with an alternative, non-study provided regimen. Retreatment options are outlined in the Manual of Procedures (MOPS).

Participants who meet criteria for Step 2, but opt out of therapy will continue study visits on the Step 1 schedule.

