#### 6.2.5 Study Completion Evaluations

For those not proceeding to Step 2, the final study visit occurs at study week 28.

For those proceeding to Step 2, the final study visit occurs 12 weeks after re-treatment completion, with extension to 24 weeks after re-treatment completion if the participant receives RBV.

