##### HCV Virologic Failure

Participants who experience for HCV virologic failure (see details in [section 6.2.4](#)) in Step 1 will have the option to enter Step 2 for re-treatment, otherwise the participants will be followed on study/off treatment through week 28.

Participants who permanently discontinue study treatment for HCV virologic failure (see details in [section 6.2.4](#)) in Step 2 will be followed through 12 weeks (or 24 weeks, if RBV given) after the treatment completion. No further treatment will be provided by the study.

Virologic evidence of recurrence, defined as HCV RNA  $\leq$ LLOQ at end of treatment but HCV RNA quantifiable ( $>$ LLOQ) during follow-up, will require confirmation and should be performed in real time at the designated VSL as soon as possible but within 2 weeks after determination of initial observation. The results will be provided to the co-chairs and site investigators within 2 weeks of specimen receipt.

#### HCV Virologic Response-Based Treatment Stopping Criteria in Step 2

The following on-treatment HCV virologic response-based treatment stopping criteria will be utilized for all participants in Step 2:

- Confirmed increase in HCV RNA  $>$ LLOQ if HCV RNA previously declined to  $\leq$ LLOQ (detected or not detected) AND
- Confirmed  $\geq 1 \log_{10}$  IU/mL HCV RNA on-treatment increase from nadir
- Confirmation will be required for all stopping criteria and should be performed as soon as possible but within 2 weeks after determination of initial observation (see HCV Recurrence/VF Confirmation in [Table 6.1-2](#)).

HCV RNA measurement to confirm treatment failure will be performed in real-time at the designated VSL and the results will be provided to the site PI within 2 weeks of specimen receipt. If treatment failure is confirmed, then all study treatment should be stopped. However, participants should be followed as per [section 6.2.6](#).

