### 10.6 Analyses

The primary efficacy objective will be addressed by estimating the proportion of participants who achieve SVR12 ([section 10.2.1.1](#) describes this primary endpoint). All enrolled participants who receive any study treatment will be included in the primary analysis. A two-sided 90% CI will be calculated around the estimated SVR12 proportion using the Wilson method for binomial data. If this CI is entirely above 80%, then it will be concluded that there is evidence that the underlying SVR12 proportion is greater than 80%.

For the primary safety analysis, the AEs occurring after initiation of study treatment through the study visit occurring 4 weeks after the treatment completion will be summarized. The proportion of study participants with AEs will be estimated with a two-sided 95% CI around the estimate. As a secondary analysis, all reported AEs (which include events that occur after the time frame defined for the primary safety analysis) will be summarized. A two-sided 95% CI will also be provided for the proportion of study participants with AEs. The Wilson method will be used.

As a secondary analysis, SVR12 will be assessed in the analysis set that excludes participants who discontinued the study early for reasons clearly not related to the study

treatment and participants who became re-infected with HCV prior to SVR12 visit. Reasons not related to study treatment include: participant moved away, participant cannot get to the clinic, participant cannot be located. The analysis will use methods similar to the primary analysis. SVR12 results will also be described separately by HIV-1 infection status.

The secondary HCV RNA endpoints (HCV RNA <LLOQ at study visits) will also be assessed with proportion estimates with two-sided 90% CI using the Wilson method, similar to the primary efficacy analysis on SVR12.

Tolerability failures and virologic failures, as defined in [section 10.2.2](#), will be listed and described. A tolerability failure listing will be accompanied by treatment duration and the associated AE(s). Listings on virologic failure will be accompanied by HCV RNA results and any available information on HCV genotype/subtype, RAS and phylogenetic results.

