#### 3.2 Secondary Outcome Measures

1. [For Secondary Objectives 1 and 3] HCV RNA <LLOQ (TD or TND) at study visits, using the visit windows as defined in Protocol Section 6.0.
2. [For Secondary Objective 2] Virologic failure, defined as failure to achieve unquantifiable HCV RNA and confirmed increase in HCV RNA  $>1 \log_{10}$  from on-treatment nadir.

Outcomes at study visits after Week 28 will be obtained after the primary completion date (PCD) and will be addressed in a separate analysis plan. For the outcome measures obtained after PCD, the results will be posted to ClinicalTrials.gov after the initial results submission and no later than one year after the last participant's study completion.

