## 4 Statistical Principles

### 4.1 General Considerations

- The analysis will include all participants who initiate the study treatment.
- Baseline refers to study evaluation closest to Week 0 prior to initiation of study treatment.
- For summaries of outcomes at specified study visits (e.g. HCV RNA at study visits for Secondary Outcome Measure 1), study visit windows as specified in Protocol Section 6.0 will be used, unless specified otherwise. In the event of multiple results within a study window, the result closest to the scheduled evaluation week based on the time since study entry randomization date will be used.
- Continuous variables will be summarized with min, Q1, median, Q3, and max, unless specified otherwise. Mean and standard deviation may also be reported, if there are sufficient numbers to make these statistics meaningful.

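### SVR24 has no stated scoring for participants who fail Step 1 and enter re-treatment before week 28, and the available-data rule would drop these known failures from its denominator.

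*SAP*

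**What the plan says.** SAP 2.3.2 names week 28 (SVR24) among the secondary HCV RNA time points. SAP 3.2 defines the outcome as HCV RNA below the LLOQ "at study visits, using the visit windows as defined in Protocol Section 6.0".

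The rules that count a missing value or early discontinuation as failure, and the rule that fills a gap from the neighbouring results, are written in SAP 3.1 and 4.2 for SVR12 only. For the visit endpoints, SAP 4.2 says "All available data for the indicated study visits from the participants who initiate the study treatment will be used in the analysis", and adds that the number with data will be given for each analysis.

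Two other lines bear on the denominator. SAP 4.1 says "The analysis will include all participants who initiate the study treatment". Protocol 10.6 says the visit endpoints get proportions with 90% Wilson intervals, "similar to the primary efficacy analysis on SVR12".

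On follow-up, protocol 3.0 sends participants with recurrence or virologic failure by week 16 to Step 2. Protocol 6.2.5 says "For those not proceeding to Step 2, the final study visit occurs at study week 28". Those who decline re-treatment stay on the Step 1 schedule: "Participants who meet criteria for Step 2, but opt out of therapy will continue study visits on the Step 1 schedule" (protocol 3.0). Protocol 6.2.6 says the same for virologic failure: "will have the option to enter Step 2 for re-treatment, otherwise the participants will be followed on study/off treatment through week 28".

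**The concern.** The missing week 28 values are produced by the outcome itself. A participant who fails Step 1 and starts re-treatment moves to the Step 2 visit schedule and has no Step 1 sample at week 28. Under an available-data rule, SVR24 becomes the response proportion among people not already removed for failing, and it can exceed SVR12 in the same trial.

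SVR24 belongs to the secondary outcomes meant for the primary manuscript and ClinicalTrials.gov (SAP 1.1). Giving the number with data shows a smaller denominator, but does not by itself show that the absent participants are failures. The same rule applies to the HIV-1 subgroup (SAP 5, item 12c), which may have as few as 10 participants.

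**Working it through.** **Inputs from the documents.** n = 44; SVR12 success rule of at least 40/44; two-sided 90% Wilson interval (protocol 10.4 and 10.6, SAP 2.4 and 4.2). Week 28 window of -7 to +28 days (protocol 6.2.3). Step 2 entry up to 270 days after the confirmatory sample (Letter of Amendment #4). HIV-1 minimum of 10.

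**Assumptions.** The number of Step 1 failures and the number k who enter Step 2 before a week 28 sample are not given, so both are varied. Responders are taken to have complete week 28 data and no late recurrence.

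**Formula.** With p = x/n and z = 1.645, the Wilson limits are [p + z²/(2n) ± z·√(p(1-p)/n + z²/(4n²))] / (1 + z²/n).

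**The plan's own figures.** For 40/44: p = 0.9091, z² = 2.706 and 1 + z²/n = 1.0615. The centre is (0.9091 + 0.0307)/1.0615 = 0.885 and the half-width 0.073, giving 81.2% to 95.9%, as in protocol Table 10.4-2. The lower limit for 39/44 is 78.4%, so 40 is the smallest passing count. The exact binomial power of that rule at a true 95% is 93.3% (stated: 93%), with a one-sided error of 0.044 at 80%.

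**Who is affected.** The week 28 window runs from day 196 - 7 = 189 to day 196 + 28 = 224. A confirmatory sample at the nominal week 16 visit (day 112) allows Step 2 entry up to day 112 + 270 = 382, so entry can fall before or after week 28. Three groups still give a Step 1 week 28 result: those who decline re-treatment, those who enter Step 2 after their week 28 sample, and those whose recurrence comes after week 16, which does not lead to Step 2. Hence k can be anything from 0 to the number of failures.

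**SVR24 with 4 failures by week 16 (the most that still meets the SVR12 rule).**

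| k absent at week 28 | x/n | Estimate | 90% CI |
|---|---|---|---|
| 0 | 40/44 | 90.9% | 81.2 to 95.9 |
| 1 | 40/43 | 93.0% | 83.8 to 97.2 |
| 2 | 40/42 | 95.2% | 86.6 to 98.4 |
| 3 | 40/41 | 97.6% | 89.8 to 99.5 |
| 4 | 40/40 | 100% | 93.7 to 100 |

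**Other failure counts, all counted against all absent.** Two failures: 42/44 = 95.5% (87.2 to 98.5) against 42/42 = 100% (93.9 to 100). Eight failures: 36/44 = 81.8% (70.5 to 89.4) against 36/36 = 100% (93.0 to 100). The more failures there are, the larger the possible gap.

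**HIV-1 subgroup of 10 with one such failure.** 9/10 = 90.0% (65.2 to 97.7) if counted; 9/9 = 100% (76.9 to 100) if dropped.

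**Supplementary SVR12 (minor).** If one documented relapser is removed as an unrelated dropout, 39/44 (lower limit 78.4%) becomes 39/43 = 90.7% (80.8 to 95.8).

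**The case against.** The best reply is that SAP 4.1 and protocol 10.6 already settle the denominator: everyone treated is in the analysis, and the visit endpoints follow the SVR12 approach, in which failures count as failures. A denominator of 44 is a fair reading, and a reader should not infer that the plan prescribes dropping these participants. But neither line says what value someone with no week 28 result receives. The protocol 10.6 phrase follows a description of proportions and Wilson intervals, so it may cover only the method of estimation. If failure scoring was intended, the available-data sentence contradicts it.

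The consequences are also limited. SVR24 carries no success threshold, and SVR12 on all treated participants will stand beside it. The plan also includes a CONSORT diagram, listings of virologic failures and a description of the reasons for SVR failure. A careful reader could reconstruct the position. That lowers the stakes but does not define the outcome. The Analysis Implementation Plan may hold a rule, although an outcome-defining rule belongs in the SAP.

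Two stronger readings are tempting.

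- One is that undetectable samples taken during re-treatment could count as week 28 successes, because SAP 4.1 says only that "the result closest to the scheduled evaluation week based on the time since study entry randomization date will be used". The documents do not support this as the intent: visit windows are set separately for each step (protocol 6.2.3), and re-treatment response is its own outcome (protocol 10.2.3.5). No sentence excludes such samples, however, so one line is worth adding.
- The other is that the supplementary SVR12 exclusion has no time limit, so that responders who leave after SVR12 would be removed. The SAP 4.2 bullet does omit a limit, but the bullet before it speaks of leaving before the SVR12 visit, and protocol 10.1 sets that limit expressly. What stands is that no version of the exclusion bars removal of a participant with documented relapse. The protocol Schema's replacement condition, which concerns participants not evaluable for SVR12, suggests that such removal is not intended.

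**Conclusion.** The point holds as an unresolved conflict over how SVR24 is scored. The available-data sentence, followed literally, removes known failures from the denominator; the lines pointing to all treated participants give no score for them. With 4 assumed failures in 44, the estimate lies between 90.9% and 100%. The upper figure is a bound, reached only if all four enter Step 2 before a week 28 sample; it is not a forecast. The size rests on assumed counts of failures and Step 2 entrants, and on complete week 28 data for responders.

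The primary SVR12 analysis, its 40/44 rule and the stated power are unaffected. The supplementary SVR12 wording is a minor matter of alignment. This should be fixed before database lock. Confidence is medium, because the Analysis Implementation Plan was not seen.

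**What to change.** Add to SAP 3.2 and 4.2, for SVR24 overall and in the HIV-1 subgroup:

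1. A participant with confirmed Step 1 recurrence or virologic failure who enters Step 2 before a Step 1 week 28 sample stays in the denominator as a non-responder. Re-infection is included, as in the primary SVR12 analysis.
2. A Step 1 week 28 result observed before Step 2 treatment starts is kept as observed, including for those who decline re-treatment.
3. HCV RNA collected after Step 2 treatment starts is not used for any Step 1 outcome.

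As a minor wording change, align the supplementary SVR12 dropout exclusion in SAP 4.2 and 5 and protocol 10.6 with protocol 10.1: the participant left before the SVR12 evaluation for reasons clearly unrelated to study treatment. State that it does not remove anyone with documented relapse, undefined post-treatment viremia or virologic failure. The separate re-infection exclusion is unchanged.

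The cost is a few lines of text before database lock, with no new data or visits. The downside is that the reported SVR24 may be less favourable.
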